- reduced appetite and therefore dietary intake [3-6], resulting in lack of dietary amino acids - a key anabolic stimulus [7],
- muscle tissue catabolism during haemodialysis [8, 9], reflected by increased urea production [10] and amino acid efflux from muscle [11],
- physical inactivity, anxiety and depression [12, 13], and the
- presence of other co-morbidities associated with muscle wasting, such as diabetes and heart disease [12].

In addition, increased systemic inflammation, a frequent complication in the haemodialysis population, has been postulated to be a primary driver of skeletal muscle loss [12, 14]. To exemplify the magnitude of this problem, it has been reported that people on haemodialysis lose an average of 6.4 kg of lean tissue mass over 20 weeks, with associated significant reductions in muscle strength. In addition, and key to the research proposed herein, systemic inflammation was shown to markedly accelerate these muscle mass losses [15].

Provision of dietetic advice and high-energy/high-protein conventional oral nutritional supplements (ONS) to people on haemodialysis has previously shown to improve postabsorptive plasma amino acid profiles, body mass index (BMI), and serum albumin and prealbumin levels [16, 17]. Despite this, conventional ONS have not been proven successful in stimulating muscle protein synthesis, and consequently in increasing skeletal muscle mass [18]. Therefore, achieving improvements in skeletal muscle mass in the haemodialysis population is challenging. In part, this appears to relate to non-adherence [18, 19]. Our previous experience, based on both research studies and clinical practice, is that the taste of some conventional ONS (often described as too sweet) is commonly cited by people on haemodialysis as a reason for non-adherence to prescribed supplementation regimes [19]. In addition to the challenge of long-term adherence to conventional ONS, the persistent systemic inflammation seen in people receiving haemodialysis plays a major role in causing "anabolic resistance", a condition that inhibits improvements in skeletal muscle mass despite an increase in dietary energy and protein intake/availability [20].

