Immuno-nutrition supplements are high in energy and protein (similar to conventional ONS), but also contain a unique combination of nutrients (i.e., omega-3 fatty acids, L-arginine and nucleotides), each acting in a complementary way to suppress inflammation, while concomitantly enhancing immune function [21]. Immuno-nutrition supplements (specifically Oral Impact®, Nestle) have been mostly used in pre-surgical settings, and previous studies conducted in cancer populations have reported a decrease in post-operative infections and length of hospitalisation, underpinned by evidence of a decrease in systemic inflammation [22].

This will be the first study to explore the potential effect of an immuno-nutrition supplement (Oral Impact®, Nestle) to address systemic inflammation in people receiving haemodialysis. The findings of this pilot study will help to design a randomised controlled clinical trial investigating whether a treatment bundle of resistance exercise training and immuno-nutrition supplementation can improve skeletal muscle mass, other markers of nutritional status and quality of life in people on haemodialysis.

STUDY OBJECTIVES AND PURPOSE

PURPOSE

The purpose of the present study is to investigate the impact of an immuno-nutrition supplement on systemic inflammation in people receiving haemodialysis.

PRIMARY OBJECTIVE

To investigate whether provision of an immuno-nutrition supplement decreases systemic inflammatory status in people on haemodialysis.

SECONDARY OBJECTIVES

To investigate the effect of an immuno-nutrition supplement on biochemical blood variables, body composition, dietary intake, skin autofluorescence (SAF) and muscle strength in people on haemodialysis.

DETAILS OF PRODUCT(S)

Description

Oral Impact® is a powdered oral nutritional supplement that contains a unique combination of ingredients with immuno-modulating properties, namely omega-3 fatty acids, arginine and nucleotides, as well as soluble fibre.

Manufacture

Oral Impact® is manufactured by Nestlé Health Science, Reg. Trademark of Société des Produits Nestlé S.A. OIDC 001

Packaging and labelling

Oral Impact® comes in a box that contains 5 sachets x 74g. Please see Appendix 1 for images of packaging and labelling.

Storage, dispensing and return

Oral Impact® will be stored unopened in a locked room which should be cool, dry and away from light and humidity. Access to the room will be restricted to members of the research team.

Known Side Effects

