15 participants will be recruited from the Renal Dialysis Unit at the Royal Derby Hospital. Potential participants will be approached by the clinical care team (which may include members of the research team) with reference to the inclusion and exclusion criteria. Each eligible participant will be given a Participant Information Sheet (PIS) and a minimum of 24 hours to consider whether they wish to participate in the study. At this time, the PIS will be discussed with them, any questions answered, and informed consent will be obtained by one of the investigators if they are willing to enter the study.

It will be explained to the potential participant that entry into the study is entirely voluntary and that their treatment and care will not be affected by their decision. It will also be explained that they can withdraw at any time. In the event of their withdrawal, it will be explained that their data collected so far cannot be erased and we will seek consent to use the data in the final analyses where appropriate.

If needed, the hospital interpreter and translator services will be available to assist with discussion of the study, the PIS, consent form, and be available for the duration of the study if required. The consent form and PIS will not be available printed in other languages.

Eligibility criteria

Inclusion criteria:

- CRP level >5.0 mg/L.
- Age: ≥ 18 years (no upper age limit).
- At least three haemodialysis sessions per week for ≥ 3 hours using a biocompatible dialyser.
- Able to give informed consent.

Exclusion criteria:

- Treatment with drugs that cause immunosuppression.
- Non-English speakers or those with special communication needs.
- Pregnancy, breast feeding or intending pregnancy.
- Expected survival <6 months.
- Hospitalisation at the time of screening.
- Known intolerance or allergy to ONS (or isolated ingredients).
- Pre-dialysis serum potassium >5.0 mmol/L.
- Unable to provide informed consent.

Participant Withdrawal

Participants will be withdrawn from the study if they:

- Withdraw their consent at any time.
- Become pregnant.
- Receive a kidney transplant.
- Do not adhere to the intervention; defined as $<50\%$ of the provided immuno-nutrition supplement being consumed.

Participants do not have to provide a reason for withdrawal of consent. Participants will also be withdrawn if it is deemed unsafe or is found to be impossible to proceed in the opinion of the investigators.

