Participants may be withdrawn from the study either at their own request or at the discretion of the Investigator. The participants will be made aware that this will not affect their future care. Participants will be made aware (via the PIS and consent form) that should they withdraw the data collected to date cannot be erased and may still be used in the final analysis.

Participants will not be replaced if they withdraw from the study.

Informed consent

The process for obtaining participant informed consent will be in accordance with the Research Ethics Committee (REC) guidance, Good Clinical Practice (GCP) and any other regulatory requirements that might be introduced. The investigator or their nominee and the participant shall both sign and date the consent form before the person can participate in the study.

The participant will receive a copy of the signed and dated consent form and the original will be retained in the Study records. A second copy will be filed in the participant's medical notes and a signed and dated note made in the notes that informed consent was obtained for the study. The decision regarding participation in the study is entirely voluntary. The investigator or their nominee shall emphasize to them that consent regarding study participation may be withdrawn at any time without penalty or affecting the quality or quantity of their future medical care, or loss of benefits to which the participant is otherwise entitled. No study-specific procedures will be done before informed consent has been obtained.

The investigator will inform the participant of any relevant information that becomes available during the course of the study and will discuss with them whether they wish to continue with the study. If applicable they will be asked to sign revised consent forms.

If the consent form is amended during the study, the investigator shall follow all applicable regulatory requirements pertaining to approval of the amended consent form by the REC and use of the amended form (including for ongoing participants).

STUDY REGIMEN

Once participants have given their informed consent, they will be advised to take **daily** one sachet (74 g) of the immuno-nutrition supplement (Oral Impact®, Nestle) dissolved in 125 ml of water and will be followed-up for 6 weeks.

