Participants will receive individualised (to patient needs and food preferences) dietetic advice formulated and delivered by an experienced renal dietitian under an honorary NHS research contract ([name]), who is a member of the research team and will be supervised by an NHS renal dietitian, aiming to achieve estimated nutritional requirements for people on haemodialysis (i.e., energy: 30-35 kcal/kg/day, and protein intake: 1.0-1.2 g/kg/day) [23]. Each dietetic advice provided to participants will also be reviewed by the NHS clinical renal dietitians who are members of the participants' usual clinical care team.

Consumption of the immuno-nutrition supplement will be supervised during haemodialysis sessions (thrice weekly) and self-reported (written and counting empty sachets) on non-dialysis days. Participants will receive precise oral instructions on how and when to take the supplement with close monitoring by the renal dietitian on the research team to encourage adherence to the intervention.

Three-day food diaries (i.e., one dialysis day, one non-dialysis day and one weekend day) will be completed by the participants at baseline, 3 and 6 weeks of follow-up, and will be analysed (Microdiet, Downlee Systems Ltd, UK) to assess compliance with the advice provided and to assess energy, protein and fat intake across the study period.

Data collection procedures

Hospital electronic medical records will be used to collect relevant baseline participant characteristics, including age, sex, ethnicity, time since dialysis initiation, dialysis adequacy,

current medication, presence of diabetes and history of cardiovascular disease. Information regarding educational level, occupation status, and history of smoking will be obtained by direct interview with the participants at the time of the baseline assessment. A blood sample will be taken weekly pre-dialysis after commencing the immuno-nutrition supplement to monitor serum potassium. Results from routine clinical blood tests will be recorded at baseline and 6 weeks of follow-up and will include haemoglobin, urea, creatinine, potassium, phosphate, calcium, sodium, albumin, total proteins, total cholesterol, triglycerides and CRP.

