Pre- and post-dialysis blood samples (10 mL) will be taken at baseline and 6 weeks of follow-up and centrifuged at 2000g for 20-min to obtain at least 2 mL of plasma which will be frozen and stored at -80°C for subsequent analysis of circulating systemic pro- and anti-inflammatory cytokines via the Luminex multiplex platform.

Handgrip strength (HGS) will be measured at baseline and 6 weeks of follow-up using the Takei 5401 handgrip digital dynamometer (Takei Scientific Instruments Co., Ltd., Tokyo, Japan) within the first hour of haemodialysis treatment. The highest value of 3 attempts in the non-fistula arm will be recorded as HGS.

Body composition will be assessed via bioelectrical impedance analysis (InBody 770, InBody, Leicester, UK) and BMI at baseline and 6 weeks of follow-up.

Skin autofluorescence (SAF) will be measured using a validated Autofluorescence Reader (AGE Reader, DiagnOptics, Groningen, The Netherlands) at baseline and 6 weeks of follow-up. For each participant, three measurements will be performed on the volar surface of the lower arm at ~10 cm below the elbow, ensuring that the area has normal skin without visible vessels, scars or other abnormalities. Only the non-fistula arm will be used, and readings will be undertaken within the first hour of haemodialysis treatment.

Criteria for terminating trial

In the event of major safety concerns, new information, or issues with study conduct (e.g., poor recruitment, loss of resources), termination of the study will be considered by the sponsor. In the event of study termination, unused study resources will be reallocated as appropriate.

TRANSPORT AND STORAGE OF THE TISSUES

Pre- and post-dialysis blood samples (10 mL) will be collected at intervals as described above and centrifuged. At least 2 mL of plasma will be stored at -80°C for future analysis at the University of Nottingham Centre of Metabolism, Ageing & Physiology (COMAP).

Samples and data will be stored in a linked anonymised format. Samples will be labelled using a combination of study reference, unique study identifier and cross referenced with location code numbers to permit accurate linkage to study data and the consent form.

The master database will be held by the CI in a password encrypted file.

Where participants do not agree to the future use of the samples, they will be destroyed in accordance with the Human Tissue Act, 2004.

LABORATORY ANALYSES

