Blood samples will be taken at the Renal Dialysis Unit and transferred to the local NHS laboratory (which is serviced and managed according to national UKAS standards and governance frameworks) at the Royal Derby Hospital for routine biochemistry and

haematology testing. These samples will be labelled according to NHS requirements. No DNA or RNA extraction will occur as part of this study.

STATISTICS

Statistical analyses will be performed using SPSS version 28.0. Data will be presented as mean \pm standard deviation, median (interquartile range), or percentages, as appropriate. To compare baseline versus final evaluations, a Wilcoxon test or paired t-test will be used in the case of dimensional variables, and McNemar test in the case of categorical variables. Intergroup comparisons will be performed using Mann-Whitney test or Student t-test for continuous variables and χ^2 test or Fisher's exact test for categorical variables. An alpha error of less than 0.05 will be judged to be significant. All data will be analysed on University of Nottingham computers and backed up regularly.

Sample size and justification

A formal power calculation is not appropriate for this pilot study design, and consequently, the sample size has been selected on a pragmatic basis. We will aim to recruit 15 participants in total.

Procedures for missing, unused and spurious data

All missing data will be explained. If a space on the Case Report Form (CRF) is left blank because the procedure was not done or a question was not asked, "N/D" will be recorded. If the item is not applicable to the individual case, "N/A" will be recorded. All entries will be printed legibly in black ink. If any error is made in data entry, to correct the error, a single straight line will be drawn through the incorrect entry and the correct data entered above it. All such changes will be initialled and dated. Errors will not be erased or altered by any other method. For clarification of illegible or uncertain entries, the clarification will be printed above the item, initialled and dated. Correction fluid will not be used.

Definition of populations analysed

The study will analyse the following populations:

- Safety set: All participants who underwent at least one study session.
- Full Analysis set: All participants, who participated in at least one study session and for whom at least one post-baseline assessment of the primary endpoint is available.

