- Per protocol set: All participants in the Full Analysis set who are deemed to have no major protocol violations that could interfere with the objectives of the study.

ADVERSE EVENTS

Definitions

An adverse event (AE) is any unfavourable and unintended sign, symptom, syndrome or illness that develops or worsens during the period of observation in the study.

An AE does include a/an:

1. Exacerbation of a pre-existing illness.
2. Increase in frequency or intensity of a pre-existing episodic event or condition.
3. Continuous persistent disease or symptoms present at baseline that worsen following the start of the study.

The following are recognised complications related to chronic haemodialysis and will be recorded on the CRF, but do not need to be reported separately on an AE/Serious Adverse Event (SAE) form:

- Related to dialysis: fistula bruising, dizziness, cramps, hypotension, minor bleeding.
- Hospital admission for vascular access, acute coronary syndromes, arrhythmias, stroke, pneumonia and infections.
- Death.

An AE does not include a/an:

1. Medical or surgical procedure (e.g., surgery, endoscopy, tooth extraction, transfusion); however, the condition that led to the procedure is an AE.
2. Pre-existing disease or conditions present or detected at the start of the study that did not worsen.
3. Situations where an untoward medical occurrence has not occurred (e.g., hospitalisations for cosmetic elective surgery, social and/or convenience admissions).
4. Disease or disorder being studied, or sign or symptom associated with the disease, or disorder unless more severe than expected for the participant's condition.
5. Overdose of concurrent medication without any signs or symptoms.

A SAE is any AE occurring following study mandated procedures, directly related to the treatment or intervention that results in any of the following outcomes:

1. Death.
2. A life-threatening AE.
3. Inpatient hospitalisation or prolongation of existing hospitalisation.
4. A disability/incapacity.
5. A congenital anomaly in the offspring of a participant.

Important medical events that may not result in death, be life-threatening, or require hospitalisation may be considered a SAE when, based upon appropriate medical judgment, they may jeopardize the patient or participant and may require medical or surgical intervention to prevent one of the outcomes listed in this definition.

All AEs will be assessed for seriousness, expectedness and causality:

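### Consuming under half the supplement means withdrawal from the study; if this is applied before week 6, low consumers have no primary outcome and leave the Full Analysis set.

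*Combined protocol and SAP*

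**What the plan says.** All references are to the combined protocol and SAP.

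- **Participant Withdrawal.** Withdrawal from the study is mandatory for those who "Do not adhere to the intervention; defined as" taking less than 50% of the supplement provided. The criterion stands beside withdrawn consent, pregnancy and transplant. No assessment time or window is given. The same section says withdrawn participants are not replaced and that "should they withdraw the data collected to date cannot be erased and may still be used in the final analysis".
- **Data collection procedures.** For CRP: "Results from routine clinical blood tests will be recorded at baseline and 6 weeks of follow-up". For cytokines, pre- and post-dialysis "blood samples (10 mL) will be taken at baseline and 6 weeks of follow-up". The weekly sample in between is for potassium. No sample at early withdrawal is described.
- **Definition of populations analysed.** The Full Analysis set takes participants with at least one study session and "for whom at least one post-baseline assessment of the primary endpoint is available". The per-protocol set is the part of it "deemed to have no major protocol violations that could interfere with the objectives of the study". The 50% threshold is not mentioned there, and no set is named as primary.
- **Primary Objective.** "To investigate whether provision of an immuno-nutrition supplement decreases systemic inflammatory status in people on haemodialysis".

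**The concern.** A rule about intake normally decides who enters a per-protocol analysis. Here it ends study participation. If it is applied while the study is running, the participants it affects never reach the only scheduled post-baseline measurement of the primary outcome. The Full Analysis set then becomes close to an adherers-only set, and it largely coincides with the per-protocol set as far as adherence goes. Neither would answer a question about providing the supplement.

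This matters more than usual because the design is a single group compared with its own baseline. If people eat and drink less when they are ill or when CRP is rising, removing them makes the average change look more favourable with no help from the supplement. If low intake has nothing to do with CRP, there is little selection bias, but the estimate still describes only those who took at least half. The background section supports that second possibility for conventional supplements, whose taste "is commonly cited by people on haemodialysis as a reason for non-adherence". In both cases, the randomised trial that this pilot is meant to inform loses the week-6 outcomes of early-withdrawn low consumers.

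**Working it through.** The plan gives no effect size, SD, power or expected dropout behind its 15 participants, so it has no figure to reproduce. The check traces the rules first and then illustrates size under stated assumptions.

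**1. Tracing the rules**

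| When the rule is applied | Primary values available | Full Analysis set | Per-protocol set |
|---|---|---|---|
| Before week 6 | Baseline only | Out | Out (it is a subset) |
| At the end, after the week-6 sample | Baseline and week 6 | Could stay in | Not settled; adherence is not mentioned |

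The permission to use data collected before withdrawal does not change the first row, because before week 6 the only primary value is the baseline one. The section on missing data covers how case report forms are completed, not missing outcomes. The text does not settle which row applies.

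**2. Can the rule bite early?** Intake is supervised at dialysis three times a week and self-reported on other days, so low intake is visible as it happens. One sachet daily for 6 weeks is 6 × 7 = 42 sachets, and half is 21. Supervised sachets number 3 × 6 = 18, and 18/42 = 42.9%. If all 42 are provided, a participant who takes every supervised sachet and none at home meets the withdrawal criterion.

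**3. Illustration of selection (all inputs assumed)**

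- Change in ln CRP ~ N(0, SD), so there is no true effect.
- P(withdrawn) = logistic(a + ln(OR) × change), with a solved to give the chosen withdrawal rate. OR is the factor by which the odds of withdrawal multiply per unit rise in ln CRP.
- Apparent CRP ratio = exp(mean change in those kept), by numerical integration.

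With 25% withdrawn:

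| SD of ln change | OR 1 | OR 1.6 | OR 2.7 | OR 4.5 |
|---|---|---|---|---|
| 0.6 | 1.00 | 0.96 | 0.92 | 0.89 |
| 0.8 | 1.00 | 0.93 | 0.87 | 0.82 |
| 1.0 | 1.00 | 0.89 | 0.81 | 0.76 |

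At SD 0.8 with fewer withdrawn:

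| Withdrawn | OR 1.6 | OR 2.7 | OR 4.5 |
|---|---|---|---|
| 1 of 15 | 0.98 | 0.96 | 0.94 |
| 2 of 15 | 0.96 | 0.92 | 0.90 |

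If selection runs the other way (OR 1/1.6 or 1/2.7), the ratios are 1.02 and 1.04 with 1 of 15 withdrawn, and 1.04 and 1.08 with 2 of 15.

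**4. Chance of a falsely favourable result.** Simulated trials of 15 at SD 0.8, paired t-test on those kept, two-sided p<0.05 with a decrease. Sidedness is not stated in the plan, so two-sided is assumed.

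| Withdrawn | OR 1 | OR 1.6 | OR 2.7 | OR 4.5 |
|---|---|---|---|---|
| 25% (mean 11.25 kept) | 2.5% | 4.7% | 8.1% | 12.0% |
| 2 of 15 | 2.5% | 3.7% | 5.1% | 6.6% |
| 1 of 15 | 2.5% | 3.1% | 3.6% | 4.2% |

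**5. Precision.** The 95% CI factor for the CRP ratio is exp(t(0.975, n−1) × 0.8/√n).

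- n = 15: exp(2.145 × 0.8/√15) = 1.56
- n = 11: exp(2.228 × 0.8/√11) = 1.71

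**6. Dilution.** Suppose the supplement works in adherers and not at all in low consumers. With 3 of 15 removed, the mean change in those kept is 15/12 = 1.25 times that in all 15. If low consumers have half the effect, it is 15/(12 + 1.5) = 1.11 times.

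**The case against.** The strongest reply has four parts.

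- **The harm is conditional.** It needs early application, enough low consumers, and a link between intake and CRP change. The documents establish none of these, and supervised intake with close dietetic support may keep the numbers small. This stands as a limit on size: with one or two participants affected the bias is slight, and its direction is not certain. It does not answer the gap in the text, which allows the damaging reading.
- **The estimand is debatable.** The stated purpose and the primary outcome refer to the supplement's impact and to change after treatment with it, so a first pilot may reasonably want to know what happens in people who took it. That is fair, but a per-protocol set gives that answer without discarding the other outcomes. An outcome never measured cannot be recovered later.
- **The illustration is selective.** The 12.0% figure combines the most extreme odds ratio with one assumed withdrawal rate. The model also ignores regression to the mean, although entry requires CRP above 5 mg/L. Both points stand, so the smaller rates and the reversed direction are shown above. Regression to the mean is a separate source of bias.
- **Deleting the rule leaves no stated consequence for non-adherence.** This stands in part. Whether a low consumer goes on with the supplement is a clinical matter for the investigators to state. It need not decide whether outcomes are measured.

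**Conclusion.** The concern holds. The 50% rule is a study-withdrawal criterion with no stated timing. Given the visit schedule and the definition of the Full Analysis set, anyone withdrawn under it before week 6 contributes no primary outcome to any efficacy analysis. That much follows from the text alone.

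How far the result would be distorted cannot be determined from the documents. Under the assumptions shown, the spurious CRP ratio ranges from 1.00 (withdrawal unrelated to CRP) to 0.76 (25% withdrawn, SD 1.0, OR 4.5). It lies between 0.90 and 0.98 at SD 0.8 if only one or two of 15 are affected and withdrawal goes with rising CRP, and just above 1 if selection is reversed. If intake is judged only after the week-6 sample, the problem largely disappears. The plan should be changed because the remedy is cheap and the loss cannot be repaired afterwards.

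**What to change.** 1. Take non-adherence off the list of reasons for leaving the study, and separate stopping the supplement from leaving follow-up. The decision to stop the supplement is clinical and is not addressed here.
2. Seek week-6 CRP, cytokines, handgrip strength, body composition and SAF from every consenting participant who started, whatever the intake.
3. Name as primary the set of all who started and have a week-6 value. Report how many of the 15 are missing and why.
4. Add a simple sensitivity analysis: set missing ln CRP changes to zero, then to a stated rise, and report the rise that would cancel the observed effect. For example (assumed figures), if 11 observed participants have a ratio of 0.70 and 4 missing are set to no change, the overall ratio is exp(11 × ln 0.70/15) = 0.77. The 4 missing would need a mean ratio of exp(−11 × ln 0.70/4) = 2.67 to bring it to 1.
5. Apply the 50% threshold only in the per-protocol definition, state the period over which intake is totalled, and report percentage consumed as an outcome.

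The cost is protocol wording, matching participant information if it repeats the rule, and a few extra cytokine assays. Participants already attend dialysis at least three times a week and CRP comes from routine bloods, so no visit is added. The drawback is that the average effect may look smaller.
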